The SCoRS is a rating scale that focuses on cognitive impairment and the degree to which it affects day-to-day functioning. It consists of a 20-item interview completed by both the patient and an informant. The items are rated on a 4-point ordinal severity scale. The interviewer then generated the ratings on all items based on the results of both interviews, which represented the best judgment of the patient's true impairment, after considering the patient and informant reports. Finally, the interviewer generated a global rating that is scaled on a 10-point scale (1–10). It helps clinicians evaluate the ties between cognitive impairment and poor functioning in both research settings and daily clinical practice. The SCoRS global ratings have been significantly correlated with psychosocial functioning and its functional capacity which is used as co-primary measures to predict real world functioning. It has excellent test-retest reliability, strong relation to cognitive performance, and proven sensitivity to treatment. Internal consistency for the scale was calculated by using Cronbach's alpha coefficient, which was found

to be 0.79 (Keefe, Poe, Walker, Kang, & Harvey, 2006).

Social Functioning Scale (SFS)

Social Functioning Scale (SFS) was adapted by which developed by Birchwood et al. (1990). The scale found to be useful for diagnosing deficits of the patients' functioning and for planning of the rehabilitation procedure. The scale consists of 76 items grouped into 7 domains which comprise of Social Engagement/Withdrawal, Interpersonal Behaviour, Prosocial Activities, Recreation/Pastimes, Independence-Performance, Independence-Competence, Employment/ Education. Total score of SFS ranges between 55 to 145 points. Scoring more than 115 points means good functioning. In this study, the SFS will be employed to examine real-world functional performance. The SFS will be asked to complete by the research team rather than self-rated by participant itself to obtain information on real-world performance (Bowie et al., 2008).

Schizophrenia Quality of Life Scale Revision 4 (SQLS-R4)

The SQLS-R4 a fourth revision of the original SQLS developed by Wilkinson and colleagues in 2000. It measures two domains of psychosocial feelings, and cognition and vitality in individuals with a diagnosis of schizophrenia. It can be applied in clinical research and any publication due to its impressive measurement characteristics of this tool. In this study, the SQLS-R4 which has already translated into Malay version will be used to the respondents (Taha, Ibrahim, Rahman, Shafie, & Rahman, 2012).

Outcome measures

The trial involves the most effective treatment to enhance the outcomes in the early stages of psychosis with the primary aim to improve the long-term cognitive functioning.

Baseline measures

[figure not shown]
All inclusion criteria must be met before continuing neuropsychological assessment of the BACS-M to measure the primary outcome of cognitive functioning, PANSS which will be used to assess symptomatology and psychopathology of participants, SCoRS for functional capacity, SQLS-R4, and SFS for secondary outcomes of psychosocial functions.

Study Procedure

The study will involve multidisciplinary team, which covers from assessment, interview, randomisation and intervention. The CR training will be required team of trained clinicians

including Clinical Psychologists with at least a master's degree, Psychiatrists, Occupational Therapists, and Nurses as the recruitment and training team. In fact, the person involved in this study have been provided with a 2-day training on CR and its process to ensure the fidelity of treatment will be sustained with thorough supervision. All the assessments and interview will be administered prior to randomisation into intervention programme and immediately after intervention. It followed by interview sessions of psychopathology, psychosocial and quality of life to participants. The three months follow up is considered after termination prior to study analysis as shown in the diagram.

Consolidated Standards of Reporting Trials (CONSORT) flow diagram of participants through each stage of a randomized trial.

ReMind Cognitive Training

The intervention consists of 15 sessions with the selected web based computerised cognitive training associated with homework between each session. In this program, the therapy intensity involved 2 sessions per week for 8 weeks with 15 hours to deliver an adequate treatment to improve cognitive functioning (McGurk et al., 2007a).

It also includes prominent computerised cognitive training, which leads to significant improvement concerning verbal memory, processing speed and executive function in patients with schizophrenia. During the first visit, the participant in this study will be asked to answer a set of questionnaires and to attempt a cognitive testing. Following that, participant will be randomised to one of the two arms. The arms are; Group 1: CR Therapy with targeted Processing Speed (ReMind) through selected commercial cognitive training and Group 2: standard CR.

Psychoeducation session on cognitive functions in schizophrenia will be conducted at the beginning of the program in group with discussion towards awareness on symptomatology, coping strategies and its importance in daily application. Participant will be required to attend the ReMind programme that they have been assigned to, twice a week for eight weeks with bridging group throughout the intervention. After completing eight weeks or 15 treatment sessions, whichever comes first, a set of neuropsychological, psychopathology and psychosocial questionnaires will be administered again to find out the benefits and effects that participants received from the intervention has remained at least until then. Before and after the intervention programme, they will be asked to fill up a survey questionnaire. Finally, 3 months after the intervention, the participants will be asked to come back for another follow up session.

Treatment approach

The strategic approaches CR adopting restorative and compensatory techniques with a transfer of training to other functional that integrated with vocational support. The use of drill and practice exercises that aim to restore cognitive functions is based on evidence for neuroplasticity and supported by evidence for functional change through targeted behavioural intervention. CR approaches may not rely solely on computerized exercises but involved therapist-guided instruction with verbal discussion to link the cognitive gains to everyday life. Furthermore, patient's motivation which is an important factor for rehabilitation success and is often utilized as a determining factor in the outcome of rehabilitation (Shapi'i, Mat Zin, & Elaklouk, 2015) particularly through computerized training.

Computers can be intimidating as well as inspiring because they can also be challenging for

participants who have difficulties with perceptual mechanisms, motor control, visual pursuit and scanning, and educational deficits, such as poor reading skills, or cognitive rigidity or inflexibility. Hence, various aspects of client skills is taken into account in dealing with computers relating to cognitive functioning. Therefore, the potential cognitive training of Lumosity are identified to be tailored for maximal benefit toward the objective of this study to enhance global cognitive domains effectively through targeted Processing Speed (ReMind) with the adopted NEAR model.

Each exercise adapts its difficulty level to the user's ability, which adaptively hierarchical with low initial difficulty level followed by progress in participant which difficulty level then will be increased for more complex stimuli, shorter time limits, provide hints or explanations. Immediate feedback of the score and accuracy of responses motivate participants. The transferability of cognitive training to unlearned areas seem crucial for its significant impact on functional outcome despite the scarce evidence (Bowie et al., 2008; Cella et al., 2015). Hence, this research established the effectiveness of potential cognitive exercises and wide array of outcome measures in schizophrenia population. On the other hand, the magnificence of CR is not merely on the cognitive training per se but its vital part of bridging group that expand the generalisation to real-world application of the training. It implies the most crucial mechanism of metacognition in translating the effects into changes in global functioning.

Statistical Analysis

The descriptive statistics will be used to report the participants in terms of demographic and clinical data as well as inferential analysis such as t-test analysis for mean score of the post test. Hence, the Independent Sample t-tests will be used to compare participants and controls on age, years of education and premorbid IQ. The chi-square (χ 2) test will be used to compare the difference between groups in demographic characteristics. The relationship among the BACS measures will be evaluated through Pearson correlations among the composite scores by averaging all z-scores of the six primary measures. Pearson correlation for reliability and repeated measures for the validity of the test. The mixed model one-way analysis of variance (ANOVA) between and within group of intervention is expected to compare the difference between the means of pre and post treatment. The group differences on cognitive performance then analysed by the multivariate analysis of variance (MANOVA). The treatment effect on symptom and functioning outcomes will be analysed using Multiple Linear Regression (MLR) analysis. Effect sizes of the improvement in cognitive domain and psychosocial functioning will

also be calculated. The data analyses will be done using the SPSS version 22. All available data who met entry criteria will be analysed, which provided all outcomes on an intention to treat analysis (ITT) approach, assuming data which missing at random, including any significant predictors (Anaya et al., 2012).

Ethical Consideration

This study will be conducted in compliance with ethical principles outlined in the Declaration of Helsinki and Malaysian Good Clinical Practice Guideline. All potential participants will be enrolled in the study of cognitive remediation for first episode psychosis as defined in inclusion criteria. As the study involves UKM Medical Centre and government hospitals such as Kuala Lumpur Hospital, Kajang Hospital and Putrajaya Hospital, hence the approval from Ethics Committee of UKM and Ministry of Health (MOH) Malaysia ethical board (NMRR) have been obtained.

For ethical purposes, it is important to ensure participants that their data will be kept confidential and will be used only for the purpose of the research and will not be utilized for any personal purpose. The participants will receive information on the trial both verbally and inwritten form. Written informed consent will be obtained from each participant before inclusion. It is emphasised that participation in the study is voluntary and that the participant can withdraw his or her consent at any time without consequences for treatment possibilities. The sponsor may decide to terminate the study at any time. Participants will be informed if thestudy is terminated and follow-up visits will be arranged if needed.

There are no known risks for this treatment. Other treatments that already received (if any) should be continued as usual and they will not affect the treatment programme. There may or may not be any benefits to them. Study procedures will be provided at no cost to the participants. Information obtained from this study will help improve the treatment or management of other patients with the same disease or condition.

Publication

The final study results will be submitted as a manuscript for publication. No restrictions on publication exist. This information will be made available to the recruitment clinics and research participants.

Discussion and Conclusion

The result of the study promotes further evidence for integrated treatments that indicate the prognosis of adjunct CR by adding targeted cognitive process of processing speed through ReMind to enhance cognitive functioning and functional outcomes in patients with FirstEpisode Psychosis with the use of strategies and other approaches for recovery. The prospective cognitive training exercises is highly recommended to optimize variance and viable tools in ReMind programme in Malaysia for global cognitive gains besides the effect in symptomatology and functional capacity. The metacognitive mechanism, which the highlights despite the main study could be the active ingredients of the most effective recovery strategies to produce real-world functioning in future. Moreover, fidelity of delivery remains as one of the concerns in this study to make it evidence-based clinical practice.

Timeline

It is important to demonstrate that the project has been completed within the time allocated. Timeline considers all phases of the project including conducting a literature review, obtaining ethical clearance, writing up results and final reports.

Acknowledgements

The study has been registered through the National Medical Research Register (NMRR-16-598-29797) and Trial Registration (ISRCTN17220814). The approval to conduct the program was obtained from the Ethics Committee of Universiti Kebangsaan Malaysia (NN-2016-037) and the Ministry of Health (MOH) through the Medical Research Ethics Committee (MREC). The funding for the study grant was provided by the Centre for Research and Instrumentation (CRIM), Universiti Kebangsaan Malaysia through Geran Galakan Penyelidikan (GGP-2017-062). The data findings described in the manuscript is fully accessible without restriction, with rare exception.

Competing interests

There is no potential conflict of interest in relation to this article.

GANTT CHART FOR PhD COMPLETION

TASK TO BE PERFORMED/ YEAR		2015/2016 SEM 1					2015/2016 SEM 2						2016/2017 SEM 3						2016/2017 SEM 4					2017/2018 SEM 5					2017/2018 SEM 6					2018/2019 SEM 7			
	9	1 0	1 1	1 2	1 2	3	4	5	6		7 8	9) (1 0		1 2	1 2	3	4	5	67	7 8	9	1 0	1 1	1 2	1	2	3 4	1 5	6	7 8	9	1 0	1 1	1 1 2	2
Identify Research Area/ Problem identification																																					
Analysis & Justification																																					
Literature review																																					
Developing objectives and hypotheses																																					
Choose variable																																					
Choose type of study & sampling technique																																					
Formulate Research (questions, design & strategy) and select methods																																					
Write research proposal																																					
Negotiate access																																					
Submit proposal																																					
Defence Proposal																																					
Ethical consideration																																					
Applying research grant/ fund																																					
Pre-testing (Pilot Study) & Sampling																																					
Preparing 1 st journal publication																																					
Validation study/ NEAR software development																																					
Data collection																																					
Follow up																																			\square		
Data analysis & Preparing 2 nd journal publication																																					
Thesis Report writing 1st draft																																					
2nd draft report																																					
Viva Voce						1														1															\square		\square
Thesis Correction & Final submission																																					П

BUDGET OF THE STUDY

PORTION OF BUDGET									
MAIN ITEM	JUSTIFICATION	AMOUNT/ QUANTITY	AMOUNT (RM)						
Research Material & Supply 1) Kertas, Alatulis, Bateri	Untuk kerja-kerja perkeranian, penyelidikan dan pengumpulan data	RM 1500	RM 1500						
2) Ink	Untuk mencetak instrument dan borang berkaitan penyelidikan dan laporan	RM 2500	RM 2500						
3) Upah dan Elaun	Pengumpulan Data, Transkrip dan kemasukan data	1 GRA x 24 bulan	RM 43200						
4) Perisian Kognitif	Pembangunan Perisian Processing Speed	RM 7000	RM 7000						
5) Mesin Cetak	Untuk mencetak pelbagai instrumen dan borang penyelidikan	RM 500	RM 500						
6) Penilaian Psikologi	Untuk pentadbiran dan penilaian bagi skala klinikal	RM 5000	RM 5000						
TransportationKutipan Data danMesyuarat/Perbincangan denganagensi luar	Memastikan kajian berjalan lancar dan diselaraskan dengan sempurna Memenuhi KPI bagi penyelidikan	RM 1500	RM 1500						
Menghadiri Persidangan		RM 3000	RM 3000						
	J	UMLAH RM : TOTAL RM :	RM 64, 200.00						

REFERENCES

- Bartholomeusz, C. F., & Allott, K. (2012). Neurocognitive and social cognitive approaches for improving functional outcome in early psychosis: theoretical considerations and current state of evidence. Schizophrenia Research and Treatment, 2012, 815315. https://doi.org/10.1155/2012/815315

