Hence, a primary concern of this study is to investigate the fundamental role of processing speed in enhancing cognitive and functional outcomes in the first episode psychosis. The potential of such interventions will be initiating as early as possible as the great potential in the early stage is promising. It is imperative for CR and enhancement from the trained skills that generalised the social functioning and job-related accordingly. It is evidently suggestive that the most feasible and realistic cognitive training should be adopted in reducing disability and to ameliorate functional recovery for its active ingredient to attain the treatment aims effectively (Bowie et al., 2008). The vigorous approach seems to have affirmative prognosis toward significant change in real-world functioning which manifest a holistic perspective in recovery process. This innovative neuropsychological model of remediation will be more robust with a well-articulated theoretical rationale and clearly understood, induce specific mechanisms of action that are grounded in the neuroscience of learning and cognition, robust, durable change and outcome measures with impactful metacognitive strategies in generalisation beyond the trained task that consequently bring a meaningful improvements of functional outcome. The adjunctive psychosocial interventions in CR may vividly elevate widespread gains in schizophrenia.

Therefore, a study of randomised controlled trial through adjunctive CR in ReMind program that focuses on the lower targeted deficit of Processing Speed is crucial to be conducted with the primary aim to evaluate the efficacy in patients with FEP in Klang valley, Malaysia to augment global cognition and functional outcomes. It is also promising to embrace metacognition through in enhancing cognitive performance and psychosocial for higher functioning via real-world recovery.

Research Objective

Primary objective:

To evaluate the efficacy of Cognitive Remediation to determine the efficacy of Cognitive Remediation in improving Processing Speed in patients with First Episode Psychosis

Specific Objectives:

- 1. To measure the psychosocial functions of First Episode Psychosis participants after intervention.
- 2. To compare the difference between psychopathology of First Episode Psychosis before and after intervention.
- 3. To explore the psychotic symptoms, significant changes and effect of functioning among the participants during pre and post intervention

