- 4. To evaluate the influence of Processing Speed to predict the cognitive outcome in First Episode Psychosis.
- 5. To assess the efficacy of Cognitive Remediation Therapy in enhancing global cognitive domains in First Episode Psychosis and functional outcomes.
- 6. To ascertain the role of processing speed as mediator in enhancing global cognitive domains.

Research Question

- 1. How is the psychosocial functions of First Episode Psychosis participants after intervention between conventional NEAR and REMIND treatment?
- 2. What is the difference between psychopathology of First Episode Psychosis before and after intervention?
- 3. Is there any correlation between improvements in cognitive impairment and functioning outcomes?
- 4. How do the interviews with first episode psychosis participants support the quantitative results that their cognitive functioning changes during the post intervention?
- 5. Is there any significant mean difference between Processing Speed in REMIND andother cognitive domains in conventional NEAR?
- 6. How does Processing Speed affect the cognitive outcome in First Episode Psychosis?
- 7. Is there any significant difference of efficacy towards cognitive domains performance between conventional NEAR and REMIND treatment?

Research Hypothesis

In the present study, the booster cognitive remediation therapy of processing speed (REMIND) will be examined whether it is superior to conventional treatment (NEAR) in improving cognitive functioning in first episode psychosis patients which the null hypothesis is no difference between the two intervention groups.

Conceptual Framework

The Neuropsychological Educational Approach to Rehabilitation (NEAR) Model

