This single-blinded randomised controlled trial will address the efficacy of CR therapy using NEAR model by targeting processing speed in first episode psychosis. Participants' cognition, functioning and clinical symptoms will be assessed at baseline and then randomised to treatment arm or standard care of CRT as active control for 15 sessions/ over 8 weeks. All participants will be assessed again at post-randomisation assessment with 3 months follow-up. A sequential mixed methods design is considered, in which intervention will be executed in sequence followed by in-depth interview before the data could be triangulated. There will be primary outcome of improvement in global cognition and psychosocial as secondary outcome. All procedures and reporting of primary and secondary outcomes will follow Consolidated Standards of Reporting Trials (CONSORT) 2010 guidelines.

The primary purpose of ReMind study will execute intervention of CR with the use of quantitative instruments to test the eclectic theories of neuropsychological, learning, educational psychology and rehabilitation psychology to predict the treatment effect between independent variables of additional Processing Speed in NEAR treatment and global cognitive domains and functional outcomes as dependent variables in patients with FEP.

Randomisation and Allocation Concealment

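### Question 5 confounds arm with cognitive domain; separately, the efficacy objectives name no comparator although both arms receive remediation, and before-after change in psychopathology has no arm contrast

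*Protocol*

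**What the plan says.** **Question 5** (Research Question) reads: "Is there any significant mean difference between Processing Speed in REMIND andother cognitive domains in conventional NEAR".

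**Efficacy objectives.** The primary objective is "To evaluate the efficacy of Cognitive Remediation to determine the efficacy of Cognitive Remediation in improving Processing Speed in patients with First Episode Psychosis". Specific objective 5 is "To assess the efficacy of Cognitive Remediation Therapy in enhancing global cognitive domains in First Episode Psychosis and functional outcomes". Neither names a comparator.

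**Before-after objective.** Specific objective 2 is "To compare the difference between psychopathology of First Episode Psychosis before and after intervention". Research question 2 asks the same thing. Neither mentions the arms.

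**Arms.** Under Study design, participants are "randomised to treatment arm or standard care of CRT as active control for 15 sessions/ over 8 weeks". The ReMind Cognitive Training section defines Group 1 as remediation with targeted processing speed and Group 2 as standard remediation. No arm is without remediation.

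**Where the between-arm contrast is stated.** In the Research Hypothesis ReMind is to be superior to NEAR, and "the null hypothesis is no difference between the two intervention groups". Question 1 asks "How is the psychosocial functions of First Episode Psychosis participants after intervention between conventional NEAR and REMIND treatment" and question 7 asks "Is there any significant difference of efficacy towards cognitive domains performance between conventional NEAR and REMIND treatment". The sample size section uses a treated-versus-control difference on the BACS composite.

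**The concern.** A randomised comparison isolates a treatment effect when the same outcome is compared between arms at the same time. Three parts of the objectives and questions depart from that.

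- Question 5 changes the outcome as well as the arm. Any difference in level between cognitive domains, present before treatment, passes straight into the answer.
- The primary objective and objective 5 ask about remediation as such. Everyone receives it, so its effect cancels in the between-arm difference.
- Objective 2 and question 2 ask for change over time. That change combines the intervention with time, repeat assessment and the other treatments that, according to Ethical Consideration, continue as usual.

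At stake is what the trial may claim. Answered as worded, a domain difference could be read as a treatment effect, or improvement in both arms as efficacy of remediation. Randomisation supports neither conclusion.

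**Working it through.** **1. The plan's own figure.** Inputs from Sample size calculation: difference 30.6, SD 49.9, two-sided alpha 0.05, power 80%, equal arms.

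n per arm = 2 × (1.960 + 0.842)² × (49.9/30.6)² = 41.74, rounded up to 42. The stated 42 is reproduced. It is sized for a between-arm difference on one outcome, so the fault is not in the sample size.

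**2. What question 5 estimates.** Write m(S) and m(D) for the mean standardised scores under NEAR for processing speed and for another domain, and e for the effect of ReMind over NEAR on speed.

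- Question 5 contrast: [m(S) + e] − m(D) = e + [m(S) − m(D)]
- Same-outcome contrast: [m(S) + e] − m(S) = e

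The extra term m(S) − m(D) has nothing to do with treatment.

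**3. Its size when e = 0.** The Background section on processing speed in first-episode psychosis gives deficits of -1.68 (processing speed), -1.51 (problem solving and reasoning), -1.40 (sustained attention), -0.79 (verbal learning and memory) and -0.63 (visual learning and memory). Assumptions: SD 1 in each arm, scores on that same scale, and deficits unchanged at assessment. The test is a two-sided two-sample t-test at 5%, with 82 degrees of freedom, critical value about 1.99 and noncentrality gap × √(42/2) = gap × 4.583.

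| Domain in NEAR | Gap to speed (SD) | Noncentrality | Significant with e = 0 |
|---|---|---|---|
| Reasoning | 0.17 | 0.78 | 12% |
| Attention | 0.28 | 1.28 | about 25% |
| Verbal memory | 0.89 | 4.08 | 98% |
| Visual memory | 1.05 | 4.81 | over 99% |

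A valid test would give 5% in every row. The BACS as the protocol describes it covers verbal memory and reasoning but not attention or visual memory. For its working memory domain that list gives no deficit. The two rows that bear most directly on this trial are therefore 12% and 98%.

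The direction also misleads. If ReMind truly raised speed by 0.89 SD and verbal memory in NEAR stayed put, the expected question 5 difference would be (-1.68 + 0.89) − (-0.79) = 0. A large real benefit would appear as no difference.

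**4. What the arms identify for the efficacy objectives.** Let t be change from time and other care, r the effect of standard remediation, and a the effect of adding processing-speed targeting.

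- Change in ReMind: t + r + a
- Change in NEAR: t + r
- Between-arm difference: a

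The efficacy of remediation, r or r + a, is not recoverable from the between-arm difference. The Study design section names a as the contrast of interest: processing speed added to NEAR.

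**5. Before-after change in psychopathology.** Within an arm the change is t + r or t + r + a. It can be measured, but its parts cannot be separated. No figure is put on this because the protocol gives no expected change or retest figure for the PANSS.

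**The case against.** The strongest reply is that the contrast is already clear. The hypothesis, questions 1 and 7, the Study design section and the sample size all set ReMind against standard remediation. The paragraph before the primary objective speaks of remediation within the ReMind programme, so the term there may simply mean ReMind. Statistical Analysis plans a between- and within-group ANOVA, a MANOVA of group differences in cognition, and a regression for the treatment effect on symptoms and functioning, the last covering the subject of objective 2. All of this stands, and it means the remedy is rewording, not redesign. It does not rescue question 5, whose literal comparison is invalid under any analysis, nor does it supply the comparator missing from the two efficacy objectives.

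Several stronger readings are tempting and go too far.

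- A reader might infer that, with remediation in both arms, none of these items can be answered. Before-after change can be described, and the efficacy objectives become answerable once the comparator is named. Question 5's fault does not come from the active control: it would remain with an untreated one.
- A reader might infer that the hypothesis is the only estimable contrast stated. Questions 1 and 7 are also between-arm.
- A reader might group objective 1 with the before-after items. Question 1 makes it a comparison of arms. Objective 3 is worded as exploratory and is not an efficacy claim.
- A reader might infer that the protocol plans to report gains in both arms as efficacy. It does not say so; the risk lies in the wording.

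**Conclusion.** The point holds in three parts.

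1. Question 5 is uninterpretable as worded because arm and domain are completely confounded. With no treatment effect, the chance of a significant result at 42 per arm is about 98% against verbal memory, and from about 12% to over 99% over the four domains quoted. These percentages rest on SD 1 and on scores expressed on the scale of the quoted deficits. The protocol plans to average z-scores but does not name their reference group. If scores were standardised within the trial sample at baseline, the starting gap would vanish, but different domains would still be compared across arms. The confounding is certain; its size is illustrative.
2. The primary objective and objective 5, as worded, ask for an effect that randomisation in this trial does not identify. What it identifies is the added effect of processing-speed targeting over standard NEAR remediation.
3. Objective 2 and question 2 support description of change in psychopathology, not attribution of that change to the intervention.

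The arms, hypothesis and sample size are consistent with one another and need no change on this account.

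**What to change.** - **Question 5:** replace it with the between-arm difference (ReMind minus NEAR) in processing speed, and in each other BACS domain, at the same time point.
- **Primary objective and objective 5:** reword as the efficacy of ReMind compared with standard NEAR remediation, to match the hypothesis and the arms.
- **Objective 2 and question 2:** either ask for the between-arm difference in psychopathology, or label the before-after change as descriptive and keep efficacy wording out of it.

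The cost is protocol wording only: no extra participants, visits or measurements. What is given up is the claim that the trial tests cognitive remediation itself, which the two arms could not have supported.
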